3.1. Study Rationale

This study is being conducted based on the need to identify new and effective antibiotic treatment options for gonorrhea as antimicrobial resistance continues to rise worldwide (see Section 3.2) and based on the results of an open-label, dose-ranging Phase II study of gepotidacin for the treatment of adults with uncomplicated urogenital gonorrhea caused by NG.

Study BTZ116576 was a Phase II, randomized, multicenter, open-label, dose-ranging study evaluating the efficacy, safety, and tolerability of gepotidacin therapy in adult participants with uncomplicated urogenital gonorrhea caused by NG. Participants were administered single oral doses (1500 or 3000 mg) of gepotidacin on Day 1 with a Test-of-Cure (TOC) (Day 4 to 8) Visit. A total of 69 participants (1500 mg: 30 participants; 3000 mg: 39 participants) were included in the Microbiologically Evaluable Population. The primary aim of the study was to provide evidence for 95% bacterial eradication of urogenital NG in the Microbiologically Evaluable Population at the TOC Visit (cure rate) and to exclude the null hypothesis that the cure rate was 80% or less. Microbiological success was achieved by 97% and 95% of participants (lower 1-sided exact 95% confidence interval [CI] bound, 85.1% and 84.7%, respectively) in the 1500- and 3000-mg treatment groups, respectively. Microbiological success (bacterial eradication) was also evaluated for pharyngeal and rectal NG, with 1 of the 2 participants with pharyngeal NG and all 3 participants with rectal NG achieving microbiological success. In Study BTZ116576, gepotidacin was active in vitro

against the 69 baseline urogenital NG isolates recovered, with a gepotidacin minimum inhibitory concentration (MIC) range of ≤ 0.06 to $1 \mu\text{g/mL}$ and 50th and 90th percentile minimum inhibitory concentration (MIC_{50} and MIC_{90}) values of 0.12 and $0.5 \mu\text{g/mL}$, respectively. Additional study results demonstrated that some baseline urogenital NG isolates were resistant to ciprofloxacin, penicillin, and/or tetracycline.

This Phase III study (BTZ116577) aims to evaluate oral gepotidacin compared to intramuscular (IM) ceftriaxone plus oral azithromycin, a currently recommended treatment regimen, for the treatment of uncomplicated urogenital infection caused by NG in adolescent and adult participants.

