10.2. Sample Size Determination

10.2.1. Justification of Sample Size

Approximately 400 participants will be needed for the primary analysis population (i.e., the micro-ITT Population, as defined in Section 10.3) to demonstrate efficacy of gepotidacin in this study.

A conservative estimate of a 90% microbiological success rate has been assumed for ceftriaxone 500 mg IM plus azithromycin 1 g orally. Participants not returning for TOC will be considered a microbiological failure in this study.

Assuming a 90% microbiological success rate of ceftriaxone plus azithromycin and the same value for the actual success rate of gepotidacin, a sample size of 400 urogenital microbiological evaluable participants (200 participants in each treatment) will provide approximately 91% power to demonstrate noninferiority of gepotidacin and ceftriaxone plus azithromycin in adolescents and adults with uncomplicated gonorrhea caused by NG with a 0.025 one-sided significance level and a -10% noninferiority margin.

Approximately 620 participants will be enrolled and randomized 1:1 to gepotidacin and ceftriaxone plus azithromycin in order to identify approximately 400 participants that meet the definition of the micro-ITT Population.

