The rationale for this strategy is that it may be reasonable to assume that missing data due to either COVID-19 or due to microbiology samples which were taken but not able to be processed will not have been impacted by the treatment the patient received or their response to treatment. Microbiology samples may be missing for reasons due to COVID-19 (e.g., out of stability samples arriving at the local lab due to extended shipping times or lack of couriers to pick up the samples within agreed timeframes). But they may also be missing, for example, due to sample packing or mis-labelling issues at the site. In all cases a missing at random multiple imputation will be performed irrespective of the reason the sample is missing. All other missing data will be considered as a failure (i.e., non-responders), consistent with the primary analysis. Multiple imputations will be implemented with the following steps:

Step 1: Microbiological response will be imputed by multiple imputation using logistic regression models under a missing at random assumption in the Micro-ITT population. The number of imputations will be 1,000 and SEED= 116577. The variables used in the imputation model will include:

- Sex and sexual orientation (MSM, MSW, or female)
- Randomized Treatment group
- Interaction term between treatment and MIC (gepotidacin or ceftriaxone plus azithromycin) for randomized treatment. If needed, this may be refined prior to unblinding. Note: Baseline pathogen (*N. gonorrhoeae*)

isolate) will be determined by GSK Microbiology prior to unblinding and will include separate holistic reviews to:

- identify dominant isolate for participants with more than one *N. gonorrhoeae* isolate at Baseline. This selection will be completed for all participants with more than one *N. gonorrhoeae* isolate at Baseline in the micro-ITT Population, regardless of missing data and will be based on gepotidacin or ceftriaxone and azithromycin MIC value (and phenotypic profile if required) and will identify the dominant *N. gonorrhoeae* isolate for gepotidacin and for ceftriaxone/azithromycin treatment groups as these may differ. This will be documented prior to unblinding. Post unblinding, the dominant *N. gonorrhoeae* isolate for the randomized treatment will be used and the corresponding Baseline *N. gonorrhoeae* MICs will be used in the analysis.

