- Group MICs (gepotidacin or ceftriaxone and/or azithromycin) by randomized treatment which may be based on Baseline *N. gonorrhoeae* isolate. This will be documented prior to unblinding.
- Site (Sites with <10 participants in the Micro-ITT Population may be combined prior to unblinding)

Any subjects that have a missing value for one or more variables listed above will be excluded from the relevant imputation model(s). While logistic regression will be used for the imputation model, the stratified MN statistic will be used for the analysis of each imputed dataset.

Step 2: Step 1 will produce 1,000 imputed datasets with complete data. For each dataset, participants microbiological response will then be derived using the imputed and non-missing data per Section 7.1.1. We will estimate the proportion of success in each treatment group and its standard error using the sample estimates, and the difference in the proportion of success between the two treatment groups and its standard error using the MN method weighted on actual pooled strata as in the primary efficacy analysis for each imputed dataset separately. All estimated quantities (proportion of success in each treatment group, difference between two groups, and their associated standard errors) will be saved for step 3.

Note: the number of imputations may be increased if required following model checking to ensure results are not sensitive to the random number seed and/or number of imputations.

Step 3: The estimated quantities in Step 2 will be combined across the imputed datasets using Rubin's rules to provide pooled estimates for the success rate in each treatment group and for the difference in the proportion of successes between the two treatment groups. The 95% (Wald) CIs will be calculated for the proportions of successes in each arm as well as for the risk difference between the two treatment groups. Testing for superiority may occur if noninferiority is achieved. A one-sided *p*-value will be calculated.

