If there is zero between imputation variance, e.g., if there are no missing data to impute, then the methods described in Step 2 will be applied to a single instance of the complete data set and it will not be necessary to combine estimated quantities in Step 3. Note that if the extent of missing data is considered sufficiently high, this analysis may be repeated with all missing microbiological responses at TOC, i.e. irrespective of the reason for missingness, and assessed using multiple imputation logistic regression. Prior to unblinding a review with GSK Microbiology will determine appropriate groupings of MICs (gepotidacin and ceftriaxone plus azithromycin) for the purposes of this analysis.

- 4) A tipping point analysis may be performed for the primary endpoint in the Micro-ITT population to assess the impact of failure imputation of missing data on the microbiological response at TOC. The scope of missing data will be consistent with the multiple imputation analyses, specifically, if the entire TOC Visit, microbiology samples were missed due to COVID-19 pandemic, then the missed value will be imputed under the MAR assumption. If the TOC microbiology sample was taken but a result is not available for the sample for any reason, then the missed value will also be imputed under the MAR assumption. All other missing data will be considered as a failure (i.e., non-responders) per the primary analysis. The tipping point analysis will vary assumptions on the proportion of participants achieving success in the two treatment groups. For each combination of assumed success rates in the two treatment groups, the number of additional participants achieving success among subjects with missing microbiological response will be imputed by drawing from a binomial distribution.
 - A grid of paired values will be established, ranging from 0 to 1 in steps of 0.025, establishing the assumed response rates for each treatment group in participants with missing microbiological response.
 - For each pair of assumed response rates corresponding to treatment group, $(\theta_{Gepotidacin}^{(i)}, \theta_{Ceftriaxone\ plus\ azithromycin}^{(j)})$, repeat the following steps 100 times:
 - Sample additional responders among participants with missing responses by drawing from a binomial distribution, using the assumed response rate assigned to each treatment group. Sampling will be completed separately by treatment,

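### The multiple-imputation sensitivity analysis puts small-site terms in an ordinary logistic model with no rule for sites without failures, so it would not represent the missing-at-random assumption it is labelled with

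*SAP*

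**What the plan says.** SAP 7.1.6.2, item 3, Step 1 sets the model: "Microbiological response will be imputed by multiple imputation using logistic regression models under a missing at random assumption in the Micro-ITT population". The predictors are sex and sexual orientation, randomized treatment, "Interaction term between treatment and MIC (gepotidacin or ceftriaxone plus azithromycin) for randomized treatment", and "Site (Sites with <10 participants in the Micro-ITT Population may be combined prior to unblinding"). SAP 5.4.1 lists the same terms. "The number of imputations will be 1,000 and SEED= 116577".

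The imputation covers visits or samples missed because of COVID-19, and samples taken without a usable result. Other missing responses count as failures. If missing data are extensive, "this analysis may be repeated with all missing microbiological responses at TOC", whatever the reason.

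Three provisions come near the problem:
- SAP 5.4.1 lets small covariate categories be refined before unblinding. This is optional and depends on the number of participants, not of failures.
- The model check in Step 2 concerns the random seed and the number of imputations.
- The closing note to item 3 covers zero between-imputation variance, which is a different situation.

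Elsewhere the SAP does plan for cells without failures. Section 7.1.6.1 adds one half to the cells of such strata in the homogeneity test, and Section 7 adds a small constant when both arms are at 100%. The imputation model has no such protection.

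**The concern.** When every observed culture at a site is a success, the maximum-likelihood site coefficient has no finite value. The fitted coefficient grows with each iteration and its standard error grows much faster. Logistic imputation draws coefficients from a normal distribution with that mean and variance, so the drawn success probabilities at the site scatter close to 0 or 1. They average far below the observed rate. Participants at sites with no observed failure would then often be imputed as failures, which is not what missing at random implies.

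Item 3 is the plan's missing-at-random check on the noninferiority result. If its imputed rates are too low, its estimate and interval no longer answer that question, and the result could look less robust than it is. SAP 7.1.6.2 names packing and labelling problems at sites as causes of missing results, so the imputed participants may cluster in particular sites.

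**Working it through.** **Inputs from the documents.** Analysis size: "a sample size of 400 urogenital microbiological evaluable participants (200 participants in each treatment") (Protocol 10.2.1). Low end of success: "A conservative estimate of a 90% microbiological success rate has been assumed" (Protocol 10.2.1, with non-returners counted as failures). High end: "Microbiological success was achieved by 97% and 95% of participants" (Protocol 3.1, Phase II evaluable participants). The SAP does not say whether responses set to failure enter the imputation model before it is fitted. If they do, the low end is the relevant one; if only cultured participants are used, the high end is.

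**The plan's own figure.** Power = Φ(0.10/√(2·0.9·0.1/200) − 1.96) = Φ(3.333 − 1.96) = Φ(1.373) = 91.5%, against the stated 91%. The planning figures reproduce.

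**Failures available.** In 400 participants, 90%, 95% and 97% success give 40, 20 and 12 failures. With 20 site levels at 97%, at least 20 − 12 = 8 levels have none.

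**Chance that a site has no failures, pⁿ:**

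| Site size | 90% | 95% | 97% |
|---|---|---|---|
| 10 | 35% | 60% | 74% |
| 20 | 12% | 36% | 54% |

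**One such site.** Take 10 successes and no failures. After 25 Newton steps the standard error exceeds 100,000 and the drawn success probabilities average 50%. Stopped at 8 steps, they average about 62%.

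**Simulation.** Assumptions: 400 participants, the same true success rate at every site, and about 5% of responses missing completely at random, so that the correct imputed rate equals the observed rate. The model has sex/orientation, treatment, treatment by MIC and site, with coefficients drawn from N(β̂, V̂). The site layouts are assumed. Mean imputed success (ranges are across two independent sets of runs and, in the last column, across layouts):

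| True success | 40 sites of 10 | 20 sites of 20 | 10 sites of 40 | Site removed |
|---|---|---|---|---|
| 0.90 | 0.67-0.68 | 0.80-0.81 | 0.87 | 0.89-0.90 |
| 0.95 | 0.61-0.62 | 0.72-0.73 | 0.84 | 0.93-0.94 |
| 0.97 | 0.56-0.57 | 0.65-0.67 | 0.77 | 0.91-0.94 |

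A mixed layout with sites of 10 to 60 gave 0.82, 0.78 and 0.70. Stopping the fit at 8 steps, in the layouts where this was run (40 of 10, 20 of 20, mixed), still gave 0.72-0.84 at true 0.90 and 0.66-0.80 at 0.97.

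**Effect on the comparison** (40 of 10, 20 of 20 and mixed layouts; true success 0.90 and 0.97; model with site against the same model without it):
- 5% missing in each arm: the mean difference moves by about 0.2 points or less, and the lower 95% limit falls by 0.1-1.1 points. For 40 sites of 10 at 0.97, the standard error rises from 0.019 to 0.024 and the limit goes from −3.9% to −4.9%.
- 8% missing on gepotidacin and 2% on the comparator: the difference moves by up to about 2 points and the limit by up to about 3. The largest shift was 40 sites of 10 at 0.97: difference −0.5% to −2.6%, limit −4.4% to −7.4%.

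The lowest mean limit in any setting was −8.4%, still above −10%.

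**The case against.** The mechanism is not in dispute; its importance is. The strongest points on the other side are these.

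- **Noninferiority rests on the difference.** Site effects are shared by both arms under 1:1 allocation, so the bias largely cancels. This stands. Larger shifts needed an imbalance in missing data that the documents give no reason to expect.
- **Robustness is covered elsewhere.** The tipping-point analysis draws from a binomial distribution by arm over success rates from 0 to 1 and has no site term. Its text is permissive, but it is listed as Table 2.105 and Figure 2.104. The Microbiologically Evaluable analysis requires an available test-of-cure culture. This stands.
- **The size depends on unknown site layouts.** The 95-97% rates come from Phase II evaluable participants, and at the planning rate of 90% with sites of 40 the gap is only 0.87 against 0.90. This stands.
- **Small categories may be refined, and a blinded dry run is planned.** Outcomes are derived before the blind is broken (Protocol 9.1.1), so sites without failures could be noticed in time. This stands only in part: nothing requires anyone to look, the trigger is participant count, and no action is stated.

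A reader might infer that imputed success would collapse whatever the site sizes, or that the noninferiority conclusion loses its support. The documents bear out neither. The primary analysis counts missing responses as failures and does not use this model. The bias leans toward that same rule, so on average the result lies between the primary analysis and a true missing-at-random analysis.

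**Conclusion.** The imputation model is wrong as written, with modest consequences for the trial's main conclusion. For assumed sites of 10-20, mean imputed success is about 0.68-0.81 where 0.90 is right and about 0.57-0.67 where 0.97 is right. For sites of 40 at 0.90 the error is small. With balanced missing data the noninferiority comparison barely moves; about 2-3 points is reached only with imbalance such as 8% v 2%, and it then works against the arm with more imputed data. The fault is that this one sensitivity analysis would not show what its label says and could suggest a lack of robustness that is not there. Repeating it with all missing responses imputed would enlarge the effect. More imputations would not help, because they estimate the same biased quantity more precisely. All sizes rest on assumed site numbers, site sizes and missing rates.

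**What to change.** In SAP 7.1.6.2 (item 3, Step 1) and 5.4.1:
1. Remove site from the imputation model, or replace it with region or country, both already defined in SAP 5.4.2.
2. Also specify an augmented or penalised likelihood for the logistic imputation. With about 12 failures at 97%, the sex/orientation and treatment-by-MIC terms are sparse too, which is why removing site alone still left 0.91-0.94.
3. State that covariate levels with no failures are pooled before unblinding. Failures by region, country or sex/orientation can be counted without treatment codes. For terms that involve treatment, the likelihood in step 2 is the safeguard.

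Keeping site and adding only the augmented likelihood is not enough: imputed success was still 0.81-0.88 at true 0.90 in the layouts tried.

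The cost is a few lines of SAP text and one programming option. The downside is that any true between-site difference in success is not used in the imputation.

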7.3. Method of Treatment Assignment

Participants will be stratified by sex and sexual orientation combination (MSM, MSW, or females) and age (<18 years, ≥18 to 65 years, or >65 years) to ensure that treatment groups are balanced within each category. The MSM category will include MSM and bisexual males (i.e., male participants who have sex with both males and females). Within each stratum, participants will be centrally randomized in a 1:1 ratio to either gepotidacin or ceftriaxone plus azithromycin using an interactive response technology (IRT) in accordance with the randomization schedule generated by or under the direction of GSK's Clinical Statistics. Before the study is initiated, information and directions for the IRT will be provided to each study site.

Each participant scheduled to receive study treatment will receive a randomization number at the time of randomization. This randomization number will be used to identify the participant and indicate the treatment to be administered to that participant.

For those participants randomly assigned to gepotidacin, the first dose will be administered at the study site during the Baseline Visit and the second dose will be dispensed to participants during this visit for self-administration 10 to 12 hours after the

first dose (see Section 7.1). Participants randomly assigned to ceftriaxone plus azithromycin will be administered a single IM dose of ceftriaxone plus a single oral dose of azithromycin during the Baseline Visit.

Returned gepotidacin should not be re-dispensed to other participants.

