7.1.6. Statistical Analyses / Methods

7.1.6.1. Statistical Methodology Specification

The primary efficacy endpoint is culture-confirmed bacterial eradication (microbiological success) of NG from the urogenital body site at the TOC visit.

Microbiological success rate and Exact Clopper-Pearson confidence interval (CI) in each treatment group will be calculated. For the statistical analysis, three strata (subgroups) will be formed according to the combinations of levels of the sex and sexual orientation (MSM, MSW, Female) at baseline. For age strata, due to few participants in <18 years and >65 years age categories, the categories <18 years, ≥18 to 65 years and >65 years will be combined for primary statistical analysis, thereby removing the age effect from the analysis. If a participant is mis-stratified, then the actual pooled strata collected in the eCRF will be used in the analysis instead of the randomized pooled strata, unless specified. The effect of this stratification is to provide statistical control over these potentially important prognostic variables.

The adjusted estimates of the difference in microbiological success rate for the two treatment groups (gepotidacin – ceftriaxone plus azithromycin) will be calculated and summarized with 2-sided 95% CI based on a stratified analysis using Miettinen and Nurminen (MN) method.

The Miettinen-Nurminen (score) confidence limits for the treatment difference [Miettinen, 1985] are computed (SAS PROC FREQ [SAS, 2018] uses iterative computation for this). Stratum based point estimates and variances can be estimated from

these CIs. The MN estimate of the common risk difference and variance is computed by combining the point estimates and variances from the individual pooled strata using MN weights. The estimate uses inverse variance stratum weights to produce MN confidence limits for the stratum risk differences. The mathematics and algorithm of MN method can be found in the SAS procedure guide under “Summary Score Estimate of the Common Risk Difference” [SAS, 2018].

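### The 95% Wald limits for each arm's success rate in the multiple-imputation sensitivity analysis under-cover at high rates and can pass 100%; the effect is small at the 90% planning rate and touches no decision

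*SAP*

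**What the plan says.** SAP 7.1.6.2, item 3, builds the multiple-imputation analysis in three steps. For each of 1,000 completed datasets, Step 2 reads: "We will estimate the proportion of success in each treatment group and its standard error using the sample estimates". Step 3 combines these by Rubin's rules and then reads: "The 95% (Wald) CIs will be calculated for the proportions of successes in each arm". The pooled risk difference gets Wald limits too. The text gives no transformation, no truncation at 100% and no alternative for rates near 1.

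Elsewhere the SAP uses exact limits for a single arm's rate. For the primary analysis, 7.1.6.1 reads: "Microbiological success rate and Exact Clopper-Pearson confidence interval (CI) in each treatment group will be calculated". Clopper-Pearson limits are also specified for the EUCAST sensitivity analysis (7.1.6.2, item 5) and for the rectal and pharyngeal endpoints (7.2.6.1). The tipping-point analysis (7.1.6.2, item 4) presents limits for the risk difference only.

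The main version of the imputation covers only samples or visits missed because of COVID-19 and samples taken without a result. Other missing responses stay failures. If missingness is judged high enough, the SAP allows a repeat that imputes all missing responses.

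**The concern.** A Wald interval takes its width from the observed proportion. When an arm does very well by chance, the estimate is high and the estimated standard error is small, so the lower limit lands too high. When every participant succeeds, the standard error is zero. The interval is therefore least reliable at the high success rates that the documents treat as possible: Protocol 3.1 reports 97% and 95% in Phase II evaluable participants, and Protocol 5.5 cites about 99% for the comparator.

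At stake is an accurate label. The sensitivity table (SAP 12.9.6, Table 2.104) would print limits called 95% that cover less than that, err in the arm's favour, and may show an impossible upper limit.

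**Working it through.** **Inputs.** Protocol 10.2.1 plans on a success rate of 90% in both arms, a one-sided level of 0.025 and a margin of −10 percentage points. Its size and power statement is: "a sample size of 400 urogenital microbiological evaluable participants (200 participants in each treatment) will provide approximately 91% power". Protocol 7.3 sets equal allocation. The 90% already absorbs missing visits, since Protocol 10.2.1 counts non-returners as failures. So p = 0.90 and n = 200 per arm at planning.

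**The plan's own figure.** Power = Φ(0.10 / √(2 × 0.9 × 0.1 / 200) − 1.96) = Φ(0.10 / 0.030 − 1.96) = Φ(1.373) = 91.5%, against about 91% stated. The inputs are read correctly. The documents state no coverage for the Wald limits.

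**Coverage.** The per-arm Wald limits are p̂ ± 1.96 √(p̂(1 − p̂)/n). Coverage at a true rate p is the sum of Binomial(200, p) probabilities over outcomes whose interval contains p. This treats the data as complete.

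| True rate | Wald coverage | Lower limit above truth (2.5% nominal) | Upper limit above 100% | Wilson coverage |
|---|---|---|---|---|
| 90% | 92.7% | 5.7% | 0% | 95.6% |
| 95% | 92.6% | 6.2% | 0.9% | 96.7% |
| 97% | 93.3% | 5.9% | 14% | 94.4% |
| 98% | 90.8% | 8.9% | 41% | 93.3% |
| 99% | 86.5% | 13.4% | 72% | 94.8% |

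These are single points on a curve that oscillates, so averages are the fairer summary:

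- 89–91%: mean 94.0% (range 92.4–95.5%)
- 94–96%: mean 92.8% (89.8–95.2%)
- 98–99%: mean 88.3% (79.3–94.6%)

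**Where the 99% misses come from.** The chance of 200/200 is 0.99^200 = 13.4%. The Wald interval then collapses to 100%–100%. That one outcome is essentially the whole shortfall at 99%.

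**When the upper limit passes 100%.** This needs p̂ > n/(n + 1.96²) = 200/203.84 = 0.9811 with p̂ below 1, that is 197, 198 or 199 successes.

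**Examples.**

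- 180/200: 0.90 ± 1.96 × 0.02121 gives 85.8–94.2% (Clopper-Pearson 85.0–93.8%).
- 198/200: 0.99 ± 1.96 × 0.00704 gives 97.6–100.4% (Clopper-Pearson 96.4–99.9%). Wilson: centre (0.99 + 3.8415/400)/(1 + 3.8415/200) = 0.9808, half-width (1.96/1.0192) × √(0.0000495 + 0.0000240) = 0.0165, so 96.4–99.7%.

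**With imputation.** A simulation of the Rubin-pooled Wald interval used 1,000 imputations and 20,000 replicates per setting. Coverage was 93.3–95.2% at a true rate of 90%, 87.3–90.3% at 98% and 83.7–86.3% at 99%. The upper limit passed 100% in 44–52% of trials at 98% and 86–89% at 99%. The 2–20 missing values per arm are an assumption, as are missingness completely at random and imputation from a beta posterior within arm in place of the SAP's logistic model. Imputation variance does not remove the problem at high rates.

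**The case against.** The strongest reply is that nothing depends on these limits. Noninferiority and superiority are decided on the risk difference (SAP 2.4 and 7.1.6.1), and the per-arm limits are descriptive columns in one sensitivity table. Wald limits after pooling were also a recorded choice (SAP revision chronology, Amendment 1). This stands, and it sets the weight of the point. It does not make the 95% label right.

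The second reply is that the specified analysis will seldom reach 98–99%. Planning is at 90%, most missing responses remain failures in the main version, and so does use of other systemic antimicrobials. This also stands. Near 90% the average shortfall is about one percentage point, and the lower limit at 180/200 differs from Clopper-Pearson by about 0.9 points, part of which is Clopper-Pearson's own conservatism (96.7% coverage at a true rate of 90%). The higher rates become plausible mainly in the optional repeat.

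A reader might also infer that the mismatch with Clopper-Pearson is itself a fault, on the view that a sensitivity analysis may vary only the missing-data assumption. The SAP sets no such rule, the risk difference also moves from Miettinen-Nurminen to Wald limits, and Wilson limits would not match Clopper-Pearson either. The case rests on coverage and range alone.

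**Conclusion.** The per-arm limits in Step 3 are not 95% limits when success rates are high. Average complete-data coverage at n = 200 is about 94% for true rates of 89–91%, 93% for 94–96% and 88% for 98–99%. The error at the top is one-sided and favours the arm, and impossible upper limits are common from 97% upwards. This rests on 200 per arm, on reading the sample standard error as √(p̂(1 − p̂)/n), and, for the pooled version, on the assumed missing counts.

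Two stronger readings are not supported. One is that the noninferiority or superiority conclusion is affected: these limits do not enter it, and nothing here faults the pooled risk difference. The other is that the specified main analysis would cover only 87–91%: those are the values at exactly 98% and 99%, not bounds for the range between them, and such rates are unlikely while most missing responses count as failures. It is a minor improvement, worth making because it costs almost nothing.

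**What to change.** In SAP 7.1.6.2, item 3, Step 3, replace the per-arm Wald limits with the Wilson interval for multiply imputed proportions. Leave the pooled risk difference and its limits as planned. Wilson limits stay within 0–100%. At 200/200 the SAP's existing rule for zero between-imputation variance applies, and the ordinary Wilson interval gives a lower limit of 200/203.84 = 98.1%. The Wilson coverages tabulated above (93.3–96.7%) are for complete data; the multiply imputed form was not simulated.

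An equally acceptable change is to omit the per-arm limits from this table, as the tipping-point analysis does.

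Pooling on the logit scale is not a good substitute. The logit and its delta-method standard error are undefined at 200/200, and if that outcome is scored as a miss, coverage at 99% is 81.4%, below Wald's 86.5%.

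The cost is one sentence in the SAP and a few lines of code. Lower limits become slightly lower, for example 96.4% instead of 97.6% at 198/200. Sample size and the primary analysis are unaffected.
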